## 4. Definitions

**Table 2 Terminology and Definitions**

Terminology	Definition
Study Medication/Drug (SM)	AK002 or placebo administered by IV infusion.
Study Day	Study Day 1 is defined as the date on which a subject took the first dose of SM. Other study days are defined relative to Study Day 1. For visits prior to the first dose of the SM, Study Day is calculated as Visit Date – Day 1 Date. For visits after the first dose, Study Day is calculated as Visit Date – Day 1 Date +1.
Enrolled	Subject who is randomized to a treatment group.
Completer for the Study	Subject who completes visits through the Day 113 Visit and enrolls in the AK002-003X extension study OR a subject who does not enter the AK002-003X extension study but completes the Day 141 visit.

Terminology	Definition
Baseline	Baseline for non-daily assessment (eg, laboratory tests and [REDACTED]) is defined as the non-missing value collected most recent to and before the time of the very first dose of the study drug. Baseline for daily assessment (eg, ePRO) is defined as the average of all assessments prior to the first dose of the study drug. Baseline for biopsy results is found in the respective analysis section.
Prior Medication	Medication collected on the Prior/Concomitant Medication CRF, with start date prior to Study Day 1.
Concomitant Medication	Medication collected on the Prior/Concomitant Medication CRF, with end date on/after Study Day 1. Note a Prior Medication may also be a Concomitant Medication if the start date is prior to Study Day 1 and end date is on/after Study Day 1.
Treatment-emergent	Adverse events reported in the clinical database with a date of onset (or worsening) on or after the start date of the first IV infusion of the SM.
Patient Reported Outcome (PRO)	
PRO questionnaire evaluates 8 different symptoms with 10 daily questions for intensity and frequency:
 
 
• Abdominal pain intensity
 
• Nausea intensity
 
• Vomiting intensity
 
• Vomiting frequency
 
• Diarrhea intensity
 
• Diarrhea frequency
 
• Early satiety intensity
 
• Loss of appetite intensity
 
• Bloating intensity
 
• Abdominal cramping intensity
 
 
Each intensity evaluation is scored on a scale of 0=none to 10=worst possible.

PRO Total Symptom Score (TSS)	TSS is the sum of 8 (abdominal pain, abdominal cramping, bloating, nausea, vomiting, diarrhea, early satiety, and loss of appetite) weekly average symptom intensity scores.

Terminology	Definition
PRO Composite Score of Interest (CSI)	CSI is the sum of the 3 (abdominal pain, nausea, and diarrhea) weekly average symptom intensity scores of special interest.
Treatment Responder	Subject with >30% reduction in TSS score combined with a >75% reduction in eosinophils in the gastric and/or duodenal mucosa. The eosinophil count is obtained on Day 99 (Week 14) biopsy and the TSS score for the analysis will be the average of the 14 daily scores starting with the day of the last dose to the day before the end of study biopsy. If a minimum of 7 daily scores are not recorded in this nominal 14-day window, the window will be rolled back until a minimum of 7 scores are present. For patients whose biopsy is collected prior to Day 99 due to early discontinuation, the average of the last 14 days of TSS scores recorded for that patient will be used for the analysis.
Study Week	Study Week for PRO analysis is defined as 7 days a week starting from the day of first dose (Day 1).

## 5. Study Endpoints

### 5.1 Primary Efficacy Endpoint

Percent change from baseline in the number of eosinophils per HPF in gastric mucosa or duodenal mucosa at Week 14 (Day 99). For subjects who provide both gastric and duodenal biopsies, the calculation will be based on the average count of the highest readings from the Day 99/End of study biopsy that correspond in location (gastric or duodenal) to the location with the highest average count at baseline.

### 5.2 Secondary Efficacy Endpoint

#### 1st Secondary Endpoint

Proportion of Treatment Responders, defined as patients with >30% reduction in TSS score combined with a >75% reduction in eosinophils in the gastric and/or duodenal mucosa. The eosinophil count is obtained on Day 99 (Week 14) biopsy and the TSS score for the analysis will be the average of the 14 daily scores starting with the day of the last dose to the day before the end of study biopsy. If a minimum of 7 daily scores are not recorded in this nominal 14-day window, the window will be rolled back until a

minimum of 7 scores are present. For patients whose biopsy is collected prior to Day 99 due to early discontinuation, the average of the last 14 days of TSS scores recorded for that patient will be used for the analysis.

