### 3.6 Changes to Analyses Planned in the Protocol

The protocol-defined gatekeeping procedure of high dose then low dose comparison to placebo for the primary endpoint is revised to include high/low pooled, high, and low dose comparisons to placebo for the primary and secondary endpoints.

The protocol-defined treatment responder is now classified as the 1st secondary endpoint and percent change from baseline to end of treatment in TSS is now the second (2nd) secondary endpoint. Other protocol-defined secondary endpoints are now moved to the exploratory endpoints.

The protocol-defined MITT population is now replaced with Per Protocol population for efficacy analysis.

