## **6.8 Multiple Comparisons/Multiplicity Adjustment**

To control for the family-wise type-I error rate, the following testing procedures will be implemented:

1. Test the high/low dose (Treatment Groups 1 and 2) combined group against placebo (Treatment Group 3) for the primary efficacy endpoint. If  $p \leq 0.05$  then proceed to
2. Test the high/low dose combined group against placebo for the 1st secondary efficacy endpoint. If  $p \leq 0.05$  then proceed to
3. Test the high/low dose combined group against placebo for the 2nd secondary efficacy endpoint. If  $p \leq 0.05$  then proceed to
4. Test the high dose against placebo for the primary efficacy endpoint. If  $p \leq 0.05$  then proceed to

5. Test the low dose against placebo for the primary efficacy endpoint. If  $p \leq 0.05$  then proceed to
6. Repeat above Steps 4-5 for testing the 1st secondary efficacy endpoint, then the 2nd secondary efficacy endpoint.

In the above sequential testing, if any step has  $p > 0.05$  then the tests of this step and of all subsequent steps will be considered not statistically significant.

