#### 7.1.2 Per Protocol Analysis (PP) population

The per protocol population will include all randomized subjects who do not have major protocol deviations adversely affecting the data interpretation. Some examples of PP exclusion criteria are

- Did not receive at least 2 doses of study medication
- Changed dose of systemic steroids and/or started systemic steroid treatment during the study or injections of steroids in the stomach and/or duodenum (this does not include steroids used as premedication the day before and/or the day of study drug infusions).
- Received other prohibited medications (eg, IL-5 inhibitors, dupilumab) potentially impacting efficacy during study treatment

- Did not have at least 6 PROs over 14 day period at any timepoint after administration of second dose.

The study statistician along with the study team will review protocol deviations to identify subjects to be excluded from the per protocol analysis population. The PP exclusion criteria will be updated prior to the database lock and unblinding. The PP population will be specified prior to unblinding using said exclusion criteria.

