#### 7.10.3 Sensitivity Analyses of Primary Efficacy Endpoint

##### Sensitivity Analysis

In this analysis, a responder is defined as an eosinophil count  $<30$  cells/HPF. Subjects with missing eosinophil count will be considered non-responders. A logistic regression model with effects of treatment group, randomization stratum, and baseline eosinophil count will be used to analyze the between group difference. Odds ratio and the associated 95% confidence intervals are computed for the comparison of odds of achieving response in the active treatment group against the odds in the placebo group. A sample SAS code:

```
PROC LOGISTIC ;
  CLASS group stratum / PARAM=glm ;
  MODEL resp(REF='0')=group stratum base ;
  ESTIMATE 'Grp 1 - Grp 3' group 1 0 -1 ;
  ESTIMATE 'Grp 2 - Grp 3' group 0 1 -1 ;
  ESTIMATE 'Avg Grp1,2 - Grp 3' group 0.5 0.5 -1 ;
  ODS OUTPUT ESTIMATES=parmest ;
RUN ;
```

In addition to the responder analysis, a cumulative distribution function (CDF) will be plotted for the 3 treatment groups, where the horizontal axis is the change from baseline in eosinophil count (x), ranging from the smallest (negative value meaning reduction) to the largest (positive value meaning increase) observed in the trial, and the vertical axis is the percentage of patients whose eosinophil count is  $\leq x$  cells/HPF.

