### 7.11.1 Treatment Responder at End of Study Treatment

Proportion of patients with a >30% reduction in TSS combined with a >75% reduction in eosinophils in the gastric and/or duodenal mucosa will be analyzed using the logistic regression model similar to Section 7.10.2 Sensivity Analysis. The calculation of the TSS score is found in Section 5.2 1st Secondary Endpoint.

As an exploratory analysis, the analysis of the treatment responder will be repeated for select subgroups (Section 6.9) such as EG, EGE, and EG + EGE. For each subgroup, separate logistic regression analysis will be performed similar to the sensitivity analysis for the primary endpoint of Section 7.10.3. In the analysis, two active dose groups will be combined for the comparison to the placebo group.

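### The Per Protocol exclusions drop users of steroids or prohibited drugs from the gated responder test, and the responder definition has no rule for scoring them if they are kept

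*SAP*

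**What the plan says.** - **Endpoint.** SAP Section 5.2 defines the first secondary endpoint as "Proportion of Treatment Responders, defined as patients with >30% reduction in TSS score combined with a >75% reduction in eosinophils"; the biopsy part may be met in the stomach, the duodenum or both. Table 2 defines a Treatment Responder in the same way. Both places deal with sparse diary data and with biopsies taken early. Neither mentions steroids or prohibited drugs.
- **Population.** Section 3.6: "The protocol-defined MITT population is now replaced with Per Protocol population for efficacy analysis". The revision history also records that the ITT population was removed.
- **Exclusions.** Among its examples of Per Protocol exclusions, Section 7.1.2 lists "Changed dose of systemic steroids and/or started systemic steroid treatment during the study". The same bullet covers steroid injections in the stomach or duodenum and exempts steroids given as premedication around infusions. Another example is "Received other prohibited medications (eg, IL-5 inhibitors, dupilumab) potentially impacting efficacy during study treatment". The list is open: "The PP exclusion criteria will be updated prior to the database lock and unblinding".
- **Analysis.** Under Section 7.11.1 the responder proportion "will be analyzed using the logistic regression model similar to Section 7.10.2". The logistic model actually stands in Section 7.10.3. The one non-responder rule there is "Subjects with missing eosinophil count will be considered non-responders", which does not concern drug use.
- **Gate.** Step 2 of Section 6.8 tests this endpoint for the combined dose groups against placebo at 0.05.

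**The concern.** Starting a steroid or another drug that acts on the disease happens after randomization and may differ by arm. A subject excluded for it leaves both numerator and denominator, so the response rate of the arm with more use tends to rise if the users were mostly not responders. Blinded selection of the Per Protocol set prevents deliberate choice, but it does not balance use between arms.

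Widening the population would not be enough. Under Table 2 and Section 5.2, a retained subject whose eosinophils and symptoms fell while on a steroid would count as a responder. The same applies to any user whose deviation is not judged major and who therefore stays in the Per Protocol set. The gap arises from Sections 3.6 and 7.1.2 acting together with 5.2.

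The test carries weight. If step 2 fails, seven later tests cannot be declared significant: pooled TSS (1), each dose on the primary endpoint (2), and each dose on the two secondary endpoints (4).

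**Working it through.** **Inputs from the SAP.** About 60 subjects randomized 1:1:1 (Section 3.2.3), hence 40 active v 20 placebo in the pooled test. Significance level 0.05 (Section 3.5).

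**Inputs assumed.** Response rates, and the share of each arm that uses these drugs. The SAP gives neither.

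**The plan's own figure.** Section 3.5 states 87% power for 20 v 20, difference 20 points, SD 20. Noncentrality = 20 / (20 × √(1/20 + 1/20)) = 3.162 on 38 degrees of freedom. A two-sided t-test gives 86.9%, so the figure reproduces. It concerns the primary endpoint; no power is stated for the responder endpoint.

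**Formula.** With r responders, n treated and u users in an arm, none of the users a responder:
- users counted as non-responders: r / n
- users deleted: r / (n − u)

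**Expected rates and power.** Take 40% v 10%, that is 16/40 v 2/20. Power is by exact enumeration of two binomials with an unadjusted two-sided chi-square test at 0.05.

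| Deleted, active / placebo | Active | Placebo | Difference (points) | Power |
|---|---|---|---|---|
| none; users counted as non-responders | 16/40 = 40.0% | 2/20 = 10.0% | 30.0 | 73.5% |
| 15% / 0% (6 and 0) | 16/34 = 47.1% | 2/20 = 10.0% | 37.1 | 87.3% |
| 10% / 20% (4 and 4) | 16/36 = 44.4% | 2/16 = 12.5% | 31.9 | 64.1% |
| 5% / 25% (2 and 5) | 16/38 = 42.1% | 2/15 = 13.3% | 28.8 | 55.9% |
| 5% / 5% (2 and 1) | 16/38 = 42.1% | 2/19 = 10.5% | 31.6 | 73.7% |

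The 87.3% in the second row is no gain; it comes from the enlarged difference.

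**One fixed set of responders.** Take 20/40 v 4/20, with Fisher's exact test as a simple stand-in for the logistic model:
- users counted as non-responders: 50.0% v 20.0%, 30 points, p = 0.029, whatever the use in each arm
- 0 active and 4 placebo users deleted: 50.0% v 25.0%, 25.0 points, p = 0.135
- 2 and 2 deleted: 52.6% v 22.2%, 30.4 points, p = 0.044
- 8 and 0 deleted: 62.5% v 20.0%, 42.5 points, p = 0.004

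**No true difference.** At 40% v 40% with users counted as non-responders, the chi-square test rejects in 5.2% of trials. Deleting 6 active and 0 placebo users (16/34 = 47.1% v 40.0%) raises this to 8.5%.

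**If users would have responded like everyone else.** At 40% response among the six deleted active subjects, deletion leaves 40% and no bias. Counting them as non-responders gives 0.40 × 34/40 = 34%, a difference of 24 points.

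**The case against.** The strongest objection is that users are not shown to be treatment failures. A reader might infer that non-response is already known for anyone who took these drugs, but the SAP gives no reasons for use. The steroid exclusion covers any dose change, reductions included, and runs through the whole study, so it also catches use after the biopsy. The notes to Table 1 allow for subjects with asthma, atopic dermatitis or eosinophilic esophagitis, for whom a steroid course may have nothing to do with the gastric or duodenal disease. This stands. Scoring use as non-response is a convention, a composite strategy, and the last calculation above shows that it can lower the rate in subjects who would have responded anyway.

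A reader might also infer that the exclusion favours AK002. The documents do not support a direction: more use on active treatment enlarges the difference, and more use on placebo usually shrinks it and costs power.

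The size is open to challenge too. The rates are assumed, several are high and unequal, and low balanced use makes almost no difference. Power also depends on the test: with Fisher's exact test the 73.5% becomes 67%, while the plan specifies a covariate-adjusted logistic model.

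Finally, there are safeguards. The Per Protocol set is fixed before unblinding, exclusions are listed with reasons (Section 7.3), and users of prohibited medication are listed (Section 7.9.2). These allow a check afterwards, but none says how such a subject is scored.

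**Conclusion.** The point holds in this form: Sections 3.6 and 7.1.2 select on a post-randomization event in the step 2 gated test, Table 2 and Section 5.2 give no scoring rule for the same subjects if kept, and no planned analysis of this endpoint retains them.

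If no user is a responder, the assumed scenarios run from 28.8 to 37.1 points against 30, with power as low as 56% against 73%; 5% use in each arm gives 31.6 points. With the fixed counts, p falls on either side of 0.05 depending only on use in each arm. All of this rests on assumed rates of use and response.

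Two stronger readings are not supported. The fault does not lie in the endpoint definition alone, because the deletion comes from the population rules. Nor do the documents show that known failures are being discarded or that the result is biased towards AK002. This is a cheap improvement, best made before unblinding.

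**What to change.** For the first secondary endpoint only, do not apply the steroid and prohibited-medication exclusions of Section 7.1.2, and add to Table 2 and Section 5.2:

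> A subject who, after the first dose and before the end-of-study biopsy, started systemic steroids, had the systemic steroid dose increased, received a steroid injection in the stomach or duodenum, or took another prohibited medication that may affect efficacy (Section 7.1.2) is a non-responder and stays in the analysis. A subject whose steroid dose was only reduced, or whose use began after that biopsy, is kept and scored on observed data. The premedication exemption in Section 7.1.2 applies.

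The injections must be named, because lifting the steroid bullet would otherwise readmit those subjects with no rule. Keep the Per Protocol responder analysis as supportive.

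**Cost.** SAP wording and one derivation from concomitant-medication data already collected. It concerns scoring only and alters no treatment rule. Courses given for unrelated illness will count as non-response, so response rates fall slightly. The endpoint's analysis set will differ from that of the other efficacy endpoints. The remaining Per Protocol exclusions (fewer than two doses, too few diary entries) are not addressed.

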## 2. Study Objectives

### 2.1 Primary Objective

The primary objectives of the study are to evaluate:

- 1) The efficacy of AK002 in patients with EG and/or EGE as estimated by the number of eosinophils per HPF in gastric biopsies before and after receiving AK002 or placebo.
- 2) The safety and tolerability of AK002 in patients with EG and/or EGE.

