### 2.2 Secondary Objectives

The secondary objectives are to evaluate preliminarily the effects of AK002 in patients with EG and/or EGE by comparing AK002 to placebo treatment for the following parameters:

- 1) Compare treatment responders between AK002 and placebo; a responder is a patient who exhibit a >30% reduction in Total Symptom Score (TSS) (all PRO symptoms) and a >75% reduction in mucosal eosinophils.
- 2) Changes in EG/EGE symptoms in a Patient Reported Outcome (PRO) questionnaire.

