### **3.4 Hypotheses**

The hypothesis to be tested in the study is that AK002, in either one or both of the 2 doses, are different from placebo with regard to the primary endpoint of number of eosinophils per HPF in biopsies from the gastric mucosa.

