## 7.10 Analysis of Primary Efficacy Endpoint

### 7.10.1 Primary Analysis of Primary Efficacy Endpoint

The primary efficacy endpoint is the percent change from baseline to Day 99 in the number of eosinophils per HPF in gastric or duodenal mucosa with biopsy. For subjects who provide gastric or duodenal only biopsy, the calculation will be based on the average count of the highest readings from the respective mucosa at baseline and Day 99. For subjects who provide both gastric and duodenal biopsies, the calculation will be based on the average count of the highest readings from the Day 99 biopsy that correspond in location (gastric or duodenal) to the location with the highest average count at baseline. This endpoint will be summarized by treatment group.

The pooled high/low dose group and each active dose group will be compared to the placebo group in pairwise comparison using analysis of covariance (ANCOVA) model with percent change from baseline as outcome, treatment as factor, and baseline value and randomization stratum as covariates. To control for the type-I error, the Gatekeeping procedure defined in Section 6.8 will be followed.

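### Does the responder endpoint need its own site rule for subjects with both gastric and duodenal biopsies?

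*SAP*

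**What the plan says.** The SAP describes the biopsy site differently in different places.

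- **Primary objective (2.1) and hypothesis (3.4):** gastric only. Section 2.1 speaks of efficacy "as estimated by the number of eosinophils per HPF in gastric biopsies before and after receiving AK002 or placebo", and Section 3.4 of the "primary endpoint of number of eosinophils per HPF in biopsies from the gastric mucosa".
- **Primary endpoint (5.1) and its analysis (7.10.1):** gastric or duodenal. A subject with one site biopsied is measured at that site. For a subject with both, Section 5.1 takes the end-of-study readings "that correspond in location (gastric or duodenal) to the location with the highest average count at baseline", and Section 7.10.1 repeats the rule.
- **Responder objective (2.2):** "and a >75% reduction in mucosal eosinophils", with no site named.
- **Responder definition (Table 2, 5.2, 7.11.1):** Table 2 has "Subject with >30% reduction in TSS score combined with a >75% reduction in eosinophils in the gastric and/or duodenal mucosa". Section 5.2 likewise asks for a symptom response "combined with a >75% reduction in eosinophils in the gastric and/or duodenal mucosa". Section 7.11.1 uses the same site wording, and none of the three gives a rule for two biopsied sites.

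Section 6.8 makes the responder comparison for the pooled doses the second step of the sequence. If it fails, no later test can be declared significant.

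**The concern.** The authors expected subjects with disease at both sites: they wrote a two-site rule for the primary endpoint, and Section 6.9 lists EG + EGE as a subgroup. Yet the responder definition has no such rule, and Section 7.11.1 refers back to Section 5.2 only for the symptom score. Table 2 leaves the biopsy baseline to the respective analysis section, and Section 7.11.1 gives none. The same subject could therefore be a responder or not, depending on who programs the variable. With about 60 subjects, a few changes of class could decide step 2 and with it every later test. The gastric-only wording in Sections 2.1 and 3.4 adds the impression that the trial has not settled which tissue it measures.

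**Working it through.** **The plan's own figure.** Section 3.5 states 87% power for 20 against 20, difference 20 points, SD 20. A two-sided t-test at 0.05 gives 86.9%, so the figure reproduces. It does not depend on the site rule.

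**Where the readings differ.** With one biopsied site they coincide. With two, take two hypothetical subjects (counts per HPF):

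| Gastric | Duodenal | Site of 5.1 | Either site | Both sites |
|---|---|---|---|---|
| 80 to 70 (-12.5%) | 40 to 8 (-80%) | no | yes | no |
| 80 to 16 (-80%) | 40 to 20 (-50%) | yes | yes | no |

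Requiring both sites is a strained reading, since *and/or* normally means one or both. The realistic choice is the Section 5.1 site or either site. These disagree only when the site with the lower baseline clears 75%, the site with the higher baseline does not, and the symptom criterion is also met.

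**What the text leans towards.** Table 2 and Section 5.2 refer to the Day 99 eosinophil count in the singular. Section 7.11.1 borrows the logistic model of the primary endpoint's sensitivity analysis (7.10.3), which has one baseline eosinophil count as covariate. For a subject with two sites, only the rule in Sections 5.1 and 7.10.1 produces one count. This is inference; no sentence says it.

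**Size, by illustration.** The SAP gives no share of two-site subjects, no per-site response rates and no between-site correlation, so these inputs are assumed:

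- per-site response rate p = 0.50, equal at both sites;
- symptom response 0.50, independent of histology;
- share s with both biopsies, 0.25 to 0.75;
- latent correlation between sites, 0.7 to 0.

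The 40 active subjects follow from about 60 randomized 1:1:1.

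P(either) = 2p - P(both), with P(both) from the bivariate normal distribution:

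- correlation 0.7: P(both) = 0.373, P(either) = 0.627
- correlation 0: P(both) = 0.250, P(either) = 0.750

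Composite rate = 0.5 x [(1 - s) x p + s x q], where q is p for the Section 5.1 site and P(either) for either site:

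- Section 5.1 site: 0.5 x 0.50 = 25.0%
- either site, s = 0.25, correlation 0.7: 0.5 x (0.375 + 0.157) = 26.6%
- either site, s = 0.75, correlation 0: 0.5 x (0.125 + 0.5625) = 34.4%

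Active subjects classified differently = 40 x s x 0.5 x [P(either) - 0.50]:

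- low end: 40 x 0.25 x 0.5 x 0.127 = 0.6
- high end: 40 x 0.75 x 0.5 x 0.250 = 3.75

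At p = 0.10, where P(either) is 0.153 to 0.190, the same formula with 0.10 in place of 0.50 gives 40 x 0.25 x 0.5 x 0.053 = 0.3 to 40 x 0.75 x 0.5 x 0.090 = 1.4.

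The high ends need zero correlation between two sites in one subject under one intravenous treatment, which is extreme. Regression to the mean at the site chosen for its high baseline would narrow the gap further. Section 3.6 moves efficacy to the per-protocol population, so 40 is a ceiling.

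**The gastric-only wording.** Section 7.10.1 uses the readings "from the Day 99 biopsy that correspond in location (gastric or duodenal) to the location with the highest average count at baseline", which matches Section 5.1. The primary variable is therefore determined whatever Sections 2.1 and 3.4 say.

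**The case for a change.** The strongest case for a change is that a gated endpoint should be fully determined before unblinding, and this one is not. Section 7.11.1 asks only for "Proportion of patients with a >30% reduction in TSS combined with a >75% reduction in eosinophils in the gastric and/or duodenal mucosa", and reading *and/or* as either site is fair English. Step 2 would then use a different histologic measure from step 1 without saying so. Section 8 requires independently programmed datasets to match, but that check only exposes a difference in reading; it does not say which is right. The protocol may hold a rule, since Section 3.6 calls the responder protocol-defined, but Section 1 says that the SAP supersedes the protocol's statistical methods.

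This stands as a description of the text: the rule is not written down, and the lean towards the Section 5.1 site is an inference. It does not show a wrong analysis. Either rule treats all arms alike, and no inflation of the type I error follows from choosing one of them blind. Reasonable statisticians could prefer either, and the ordinary derivation specification for the responder variable has to name one.

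**Conclusion.** The concern is accurate about the wording but does not require a change to the plan. The responder definition leaves out a detail for subjects with both biopsies. The natural way to fill it is the site-specific percent change already derived for the primary endpoint; an either-site rule would also be valid. Under the assumed inputs the two readings differ for about 0.6 to 3.75 of 40 active subjects at a 50% per-site rate, and for about 0.3 to 1.4 at 10%. The true size cannot be derived from the SAP. The conclusion assumes that the derivation is settled while the study is blinded and applied identically in all arms. The gastric-only wording in Sections 2.1 and 3.4 is a clerical mismatch with no effect on any result, because Sections 5.1 and 7.10.1 agree.
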